11.2 Assessments of Adverse Events

Each adverse event (AEs) will be assessed for severity, causality, seriousness and expectedness as described below.

11.2.1Severity

| Category | Definition |
|----------|---|
| Mild | The adverse event does not interfere with the participant's daily routine, and does not require further intervention; it causes slight discomfort |
| Moderate | The adverse event interferes with some aspects of the participant's routine, or requires further intervention, but is not damaging to health; it causes moderate discomfort |
| Severe | The adverse event results in alteration, discomfort or disability which is clearly damaging to health |

11.2.2Causality

The assessment of relationship of adverse events to the procedure is a clinical decision based on all available information at the time of the completion of the case report form. As above, we do not

anticipate that any adverse events will arise from this project. However, if necessary the following categories will be used after review by the CI to define the causality of the adverse event:

The differentiated causality assessments will be captured in the trial specific SAE form.

The following categories will be used to define the causality of the adverse event:

| Category | Definition |
|----------------|---|
| Related | A causal relationship between the intervention and an adverse event is at least a reasonable possibility, i.e., the relationship cannot be ruled out. |
| Not related | There is no reasonable possibility of a causal relationship between the intervention and an adverse event. |
| Not Assessable | Unable to assess on information available. |

11.2.3 Expectedness

| Category | Definition |
|------------|--|
| Expected | An adverse event which is consistent with the information about the intervention listed in the current SmPC, Manual of Operation (amend as appropriate) or clearly defined in this protocol. |
| Unexpected | An adverse event which is not consistent with the information about the intervention listed in the current SmPC, Manual of Operation (amend as appropriate) * or clearly defined in this protocol. |

* This includes listed events that are more frequently reported or more severe than previously reported.

11.2.4 Recording of Adverse Events

All adverse events will be recorded in the CRF and on the sponsor's AE log until the participant completes the trial with a simple, brief description of the event, including dates as appropriate on the trial database.

11.3 Procedures for recording and reporting Serious Adverse Events (SAEs)

All serious adverse events will be recorded in the CRF, and the sponsor's SAE log. The AE and SAE logs will be stored in the TMF and may be subject to Sponsor monitoring and auditing.

All SAEs (except those specified in the protocol as not requiring reporting to the Sponsor) will be reported to the Sponsor within 24 hours of becoming aware. The CI/PI or designated individual will complete the Sponsor's online Research Incident Reporting Form (https://redcap.slms.ucl.ac.uk/surveys/?s=NE5dypTdFo) within 24 hours of becoming aware of the event. The Chief or Principal Investigator will respond to any SAE queries raised by the Sponsor as soon as possible.

Where the SAE is unexpected and thought to be related to the intervention, this must be reported by the Investigator to the main REC that approved the study within 15 days of the Investigator becoming aware of the event, using the non-CTIMP safety report to REC form. This form can be found on the HRA website: https://www.hra.nhs.uk/approvals-amendments/managing-your-approval/safety-reporting/. The Sponsor should be copied into this, so they are aware. Discuss with the JRO Quality Assurance team in the first instance.

11.4 Serious Adverse Events (SAEs) that do not require reporting (if applicable)

12.5 We will report any unexpected SAE to the study Sponsor. People experiencing homelessness frequently have long-standing and interacting physical and mental health conditions, substance misuse and history of TBI (22-24), undergoing accelerated ageing (16, 25-27) associated with increased service use and early death (15, 18). As such, the following events listed below describe expected disease related AEs that are not related to the trial intervention and we will not complete an SAE form and report it to the sponsor:

• For those experiencing homelessness and memory problems death, hospitalisation due to common causes related to their condition (e.g. Urinary tract infections, delirium, common infections, pneumonia) or transition to a care home as a result of progression of existing illness.

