11.1 Definitions

| Term | Definition | | | | | | |
|-----------------------|--|--|--|--|--|--|--|
| Adverse Event (AE) | Any untoward medical occurrence in a patient or trial participant, which does not necessarily have a causal relationship with the intervention involved. | | | | | | |
| Serious Adverse Event | Any adverse event that: | | | | | | |
| (SAE). | • results in death, | | | | | | |
| | is life-threatening*, | | | | | | |
| | requires hospitalisation or prolongation of existing hospitalisation**, | | | | | | |
| | results in persistent or significant disability or incapacity, or | | | | | | |
| | • consists of a congenital anomaly or birth defect. | | | | | | |

| Other 'important medical events' may also be considered | | | | | |
|---|--|--|--|--|--|
| serious if they jeopardise the participant or require an intervention | | | | | |
| to prevent one of the above consequences | | | | | |

* A life- threatening event, this refers to an event in which the participant was at risk of death at the time of the event; it does not refer to an event which hypothetically might have caused death if it were more severe.

** Hospitalisation is defined as an in-patient admission, regardless of length of stay. Hospitalisation for pre-existing conditions, including elective procedures do not constitute an SAE.

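### Section 11.4 classes listed resident events as unrelated in advance and withholds the SAE form, contradicting the case-by-case causality assessment in 11.2

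*Protocol*

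**What the plan says.** Section 11.1 makes an event serious if, among other criteria, it "results in death". Section 11.2 then sets a rule with no stated exception: "Each adverse event (AEs) will be assessed for severity, causality, seriousness and expectedness as described below". Section 11.2.2 describes how the judgement is made: "The assessment of relationship of adverse events to the procedure is a clinical decision based on all available information at the time" the case report form is completed. It offers three answers (related, not related, not assessable) and adds: "The differentiated causality assessments will be captured in the trial specific SAE form".

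Section 11.3 keeps recording and reporting apart. On recording: "All serious adverse events will be recorded in the CRF, and the sponsor's SAE log". On reporting, SAEs go to the sponsor within 24 hours, "except those specified in the protocol as not requiring reporting to the Sponsor". An SAE that is both unexpected and thought related also goes to the ethics committee.

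Section 11.4 lists the exempt events. The bullet opens "For those experiencing homelessness and memory problems death, hospitalisation due to common causes related to their condition", gives examples such as pneumonia and delirium, and ends with care-home moves caused by progression of existing illness. The lead-in says that these events "describe expected disease related AEs that are not related to the trial intervention and we will not complete an SAE form", and that they will not be reported to the sponsor.

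**The concern.** Section 11.2 makes causality a question to be answered for each event on the facts of that event. Section 11.4 answers it for a whole class before any event has happened, and withholds the form on which the answer was to be written. If 11.4 is followed, a listed event to which the intervention did contribute is classed as unrelated, and the protocol gives no way to reclassify it.

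The study has little else that would show such an event to be related. It is non-randomised with no comparator (section 4), has no data monitoring committee (12.2) and sets no criteria for stopping early (14). The training covers distress behaviours, harm minimisation, capacity and safeguarding (5.6), so it is meant to change how staff support residents. Low risk is a fair expectation, but it does not decide an individual case.

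**Working it through.** No formula applies. The check sets the sections side by side.

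1. **Which events need a causality judgement.** Section 11.2: each adverse event, no exception. Section 11.4: for the listed events the answer is already given. These conflict.

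2. **Which answers are open.** Under 11.2.2 an event is related if a causal link is at least a reasonable possibility, and may be not assessable if information is lacking. Section 11.4 leaves only one of the three categories available, whatever the facts.

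3. **Where the judgement is recorded.** Section 11.2.2 names the trial-specific SAE form. Section 11.4 says that form is not completed. The remaining records are the CRF and the logs. Section 11.2.4, which describes the adverse event record, names a short description and dates and does not name causality.

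4. **How far the exception in 11.3 reaches.** It excuses listed events from being reported to the sponsor. It does not excuse them from assessment. Section 11.4 therefore goes further than the clause it serves.

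5. **Expected versus unrelated.** Sections 11.2.2 and 11.2.3 define causality and expectedness separately. The reasons given in 11.4 (multimorbidity, substance misuse, accelerated ageing, early death) support calling the events expected in this population. They do not show that a particular event was unrelated.

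6. **Consequence for onward reporting.** The ethics report in 11.3 needs an event to be both unexpected and related. The labels in 11.4 deny both in advance. Opening causality alone would therefore not send a listed event to the ethics committee; it would also have to be judged unexpected, which the note to 11.2.3 allows when a listed event is more frequent or more severe than previously reported.

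7. **Scope of the word death.** Two readings are possible:
   - The common-causes phrase limits hospitalisation only. Every resident participant meets the description at the start of the bullet, so every resident death is exempt.
   - The phrase limits both. Only deaths from common causes are exempt, and someone must judge the cause of death first. That judgement asks whether the cause is common in this group, which is not the same as asking whether the intervention contributed.

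8. **Size.** The protocol plans 40 residents and gives no mortality or admission rate. As an illustration only, assumed mortality of 2% to 10% over follow-up gives 40 × 0.02 = 0.8 to 40 × 0.10 = 4 deaths. Hospitalisations and care-home moves would add to this by an amount the protocol does not allow one to estimate. The contradiction does not depend on these figures.

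**The case against.** The strongest reply is that 11.4 waives a form and a report, and never says that the assessment in 11.2 is waived. The SAE form cannot be the only place for causality, since 11.2 also covers non-serious events, and 11.2.2 ties the judgement to completion of the CRF with review by the chief investigator. All SAEs still enter the CRF and the SAE log, which the sponsor may audit (11.3). The trial management group reviews SAEs (12.1), a steering committee supervises the trial (12.2), and the whereabouts of residents who have left, including hospital and death, are collected at six months (6.4). Residents do not attend the sessions (5.5), and not expediting expected events in a low-risk study is a reasoned choice. Section 11.4 also opens by promising to report any unexpected SAE to the sponsor.

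Much of this stands. A reader might infer that no listed event could ever have a recorded causality judgement, that case-level causality is the only means of seeing harm, or that every resident death would go unassessed. The documents do not support those readings: a CRF-level judgement is possible, the events stay visible and countable, and the common-causes phrase may limit death. Exempting expected events from 24-hour reporting is also not the fault.

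The reply does not remove the conflict. A CRF-level judgement is of little use where 11.4 has already fixed its answer, and no section says that it should be recorded there for these events.

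**Conclusion.** The contradiction is in the text. For resident deaths, common-cause hospitalisations and the specified care-home moves, 11.4 sets relatedness by event type and withholds the form that 11.2 names, while the exception in 11.3 covers sponsor reporting only. It also treats expected as if it meant unrelated, and leaves the scope of the exemption for deaths unclear.

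The effect is limited. The events are recorded and can be counted and reviewed; what is missing is an open causality judgement and a stated place for it. The feasibility outcomes and the stop-go rule in 9.3 are untouched. The point should still be corrected, because these rules would be applied as written and the correction is cheap. The conclusion rests on the wording of 11.1 to 11.4 alone and needs no assumed event rate.

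**What to change.** Reconcile 11.2, 11.3 and 11.4 as follows:

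- Delete the statement in 11.4 that the listed events are unrelated. They can remain listed as expected.
- Record an individual causality judgement for each listed event, using the categories in 11.2.2, and name where it goes: the CRF and SAE log, or the SAE form.
- Apply the exemption from sponsor reporting only to listed events that have been assessed as not related.
- State whether the common-causes qualifier applies to death.

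A full SAE form for every death and unplanned admission is not needed to remove the contradiction; a causality field in a record that is already required would do. The cost is a change of protocol wording and a small number of extra causality entries among about 40 residents.

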11.5 Incidental Findings in Research

We do not foresee any incidental findings as part of the study.

11.6 Unblinding

This is a non-randomised study.

11.7 Reporting Urgent Safety Measures

If any urgent safety measures are taken the CI/ PI shall immediately and in any event no later than 3 days from the date the measures are taken, give written notice in the form of a substantial amendment to the relevant REC and Sponsor of the measures taken and the circumstances giving rise to those measures.

11.8 Protocol Deviations and Violations

A reportable protocol violation is a breach which is likely to effect to a significant degree:

- (a) the safety or physical or mental integrity of the participants of the trial; or
- (b) the scientific value of the trial.

The Sponsor will be notified immediately of any protocol violations during the trial conduct phase by completion of the online JRO Research Incident Reporting Form: https://redcap.slms.ucl.ac.uk/surveys/?s=NE5dypTdFo. All protocol violations must be recorded on the Protocol Violation Log and filed in the TMF.

Protocol deviations are **minor** unintended departures from the expected conduct of the study protocol/SOPs, which **does not impact** the participants' safety or compromises the integrity of the study data. E.g. a study visit date being outside the window defined in the protocol. Protocol deviations do not need to be reported to the Sponsor but should be recorded in the Protocol Deviation Log and filed in the TMF.

11.9 NHS Serious Incidents and Near Misses

We do not have any NHS trust sites.

11.10 Complaints from research participants

In the first instance, research participant complaints will be reported to the CI to investigate, as documented in the participant information sheet(s), and to the Sponsor via [contact], following the UCL Complaints from Research Subjects about UCL Sponsored Studies and Trials policy.

12.OVERSIGHT COMMITTEES

12.1 Trial Management Group (TMG)

The TMG will include the CI and trial staff. The TMG will be responsible for overseeing the trial. The group will meet approximately every 3-6 months. The TMG role, arrangements and frequency of meetings will be detailed in a TMG charter and will review recruitment figures, SAEs and substantial amendments to the protocol prior to submission to the REC.

12.2 Trial steering committee (TSC)

The role of the TSC is to provide overall supervision of the trial. The TSC will review the recommendations of the (Independent) Data Monitoring Committee (if applicable) and, on consideration of this information, recommend any appropriate amendments/actions for the trial as necessary. The TSC acts on behalf of the funder(s) and Sponsor.

We are testing a low risk intervention therefore we will not convene a Data Monitoring Committee. No interim analyses will be conducted on the data.

13. REGULATORY REVIEW AND PATIENT AND PUBLIC INVOLVEMENT

13.1 Regulatory Review

The Sponsor will ensure that the trial protocol, participant information sheet, consent form, GP letter and submitted supporting documents have been approved by the appropriate research ethics committee, prior to any participant recruitment. The protocol, all other supporting documents including and agreed amendments, will be documented and submitted for ethical and regulatory approval as required. Amendments will not be implemented prior to receipt of the required approval(s).

The study was deemed to require regulatory approval from the NHS NRES and HRA. Full approval will be obtained before the study commences.

There are no NHS sites planned for this study.

All correspondence with the Sponsor, REC and HRA will be retained. The CI will notify the Sponsor and REC of the end of the study.

It is the CI's responsibility to produce the annual progress reports when required; an annual progress report (APR) will be submitted to the Sponsor and REC within 30 days of the anniversary date on which the favourable opinion was issued, and annually until the study is declared ended.

Within 90 days after the end of the trial, the CI will ensure that the main REC is notified that the trial has finished. If the trial is terminated prematurely, those reports will be made within 15 days after the end of the trial.

Within one year after the end of the study, the CI will submit a final report with the results, including any publications/abstracts, to the Sponsor and to the REC and HRA.

13.2 Peer Review

The study has been peer reviewed in accordance with the requirements outlined by UCL:

The Sponsor considers the procedure for obtaining funding from NIHR to be of sufficient rigour and independence to be considered an adequate peer review.

The CI will conduct a risk assessment for this trial. The degree of monitoring will be proportionate to the objective, purpose, phase, design, size, complexity, endpoints and risks associated with the trial. A trial specific oversight and monitoring plan will be established for studies. The trial will be monitored in accordance with the agreed plan. The degree of monitoring will be proportionate to the risks associated with the trial. Risk will be assessed on an ongoing basis by the CI, and adjustments made accordingly (in conjunction with the Sponsor).

The CI will inform the Sponsor should he/she have concerns which have arisen from monitoring activities, and/or if there are problems with oversight/monitoring procedures. The study trial management group will meet face to face at least twice a year.

We are conducting a low risk non-CTIMP (non-clinical trial of an investigational medicinal product) therefore no criteria have been set to stop the trial prematurely.

The UCLH/UCL Joint Research Office, on behalf of UCL as Sponsor, will conduct random audits on a selection of studies in its clinical research portfolio. Monitoring and auditing will be conducted in accordance with the UK Policy Framework for Health and Social Care Research, and in accordance with the Sponsor's monitoring and audit policies and procedures.

15.TRAINING

The CI will review and provide assurances of the training and experience of all staff working on this study. Appropriate training records will be maintained in the study files.

A short training programme will be delivered by the CI to any research staff. There will be a strong practical focus on empathic listening skills, making effective use of supervision and when to ask for help. Training will emphasise the need to operate from an inclusive values base and to respect diversity and the existing knowledge and experience staff and service users. Researchers delivering the intervention will receive a bespoke training described above in section 6.1. Because of the sensitive nature of this work and the fact that researchers may witness directly or via staff accounts potentially distressing incidents, we will provide additional support that we have found has been highly valued by staff collecting similar data in previous end of life care and dementia studies. This includes 1) swift access to senior clinical researchers i.e. by mobile phone to debrief on any incidents, 2) regular confidential clinical supervision with an experienced practitioner where incidents can be discussed as can other challenging issues such as maintaining the boundary whilst doing research observations, 3) regular peer group support with other project staff.

16.INSURANCE AND INDEMNITY

University College London holds insurance against claims from participants for injury caused by their participation in the trial. Participants may be able to claim compensation if they can prove that UCL has been negligent. However, as this trial is being carried out in third sector homelessness hostels, the hostels continue to have a duty of care to the participant of the trial. University College London does not accept liability for any breach in the hostel's duty of care, or any negligence on the part of their employees.

Participants may also be able to claim compensation for injury caused by participation in this trial without the need to prove negligence on the part of University College London or another party. Participants who sustain injury and wish to make a claim for compensation should do so in writing in the first instance to the CI, who will pass the claim to the Sponsor's Insurers, via the Sponsor's office.

Hostels selected to participate in this trial shall provide negligence insurance cover for harm caused by their employees and a copy of the relevant insurance policy or summary shall be provided to University College London, upon request.

17.RECORD KEEPING AND ARCHIVING

UCL and each participating site recognise that there is an obligation to archive study-related documents at the end of the study (as such end is defined within this protocol). The CI confirms that he/she will archive the Trial Master File at UCL Maple House for the period stipulated in the protocol and in line with all relevant legal and statutory requirements. The Principal Investigator at each participating site agrees to archive his/her respective site's study documents in line with all relevant legal and statutory requirements will be archived for a minimum of 5 years from the study end, and no longer than 20 years from the study end.

The Trial Master File will be archived at UCL, in accordance with the UCL Retentions Schedule. It will be archived for a minimum of 5 years from the study end, and no longer than 20 years from study end.

18.INTELLECTUAL PROPERTY

All background intellectual property rights (including licences) and know-how used in connection with the study shall remain the property of the party introducing the same and the exercise of such rights for purposes of the study shall not infringe any third party's rights.

All intellectual property rights and know-how in the protocol, the study data and in the results arising directly from the study, but excluding all improvements thereto or clinical procedures developed or used independently of the study by each participating site, shall belong to UCL. All intellectual property rights deriving or arising from the material or any derivations of the material provided to UCL by the participating site shall belong to UCL. Each participating site agrees that by giving approval to conduct the study at its respective site, it agrees hereby to effectively assign all such intellectual property rights ("IPR") to UCL and to disclose all such know-how to UCL.

Each participating site agrees to, at the request and expense of UCL execute all such documents and do all acts necessary to fully vest the IPR in UCL.

Nothing in this section shall be construed so as to prevent or hinder the participating site from using know-how gained during the performance of the study in the furtherance of its normal activities of providing or commissioning clinical services, teaching and research to the extent that such use does not result in the disclosure or misuse of confidential information or the infringement of an intellectual property right of UCL or its funder. This does not permit the disclosure of any of the results of the study, all of which remain confidential.

